**Study Procedures, including Visits and Phone Contacts**

All participants will attend an initial in-person baseline visit at their primary care clinic where they will provide written informed consent, receive information on assigned intervention components, complete assessments, provide a breath sample for carbon monoxide (CO) assessment, and receive initial treatment based on their treatment condition. After the initial visit, study participation will include phone calls and/or additional in-person visits to provide interventions and collect data.

***Motivation Study***

This study has two phases: Motivation and Cessation. While all participants will receive Motivation treatment, participation in the Cessation phase of the research depends on whether participants decide they would like to quit smoking during the Motivation phase.

***Motivation Phase.*** After the in-person baseline session, all participants in the Motivation Study will receive assessment calls at Weeks 12, 26, 39 and 52. They will also receive 11 IVR calls over the course of 52 weeks. Participants receiving Behavioral Reduction (BR) Counseling and Behavioral Activation (BA) Counseling will receive 1 in-person session at Week 0 followed by 9 phone sessions (Table 3). Participants receiving 5Rs Motivation Counseling will receive 1 in-person session at Week 0 followed by 3 phone sessions (Table 3). Participants who are randomized to receive Nicotine Mini-Lozenge will receive 15 weeks of medication at Week 0. Participants who are still using the medication will receive more medication following the 12, 26,

## PROTOCOL

### “Breaking Addiction to Tobacco for Health (BREATHE) Study”

PI: [name], MPH, MBA; UW-CTRI Center Grant: 1P01CA180945-01.

and 38-week assessment calls. Medication use and AE assessments will occur either during the Week 3 and 5 counseling calls, or alone if the participant is not randomized to receive any counseling.

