**Table 1. Motivation Study Treatment Conditions**

Conditions	Medication Type (Mini-Lozenge)	Behavioral Reduction (BR) Counseling	5Rs Motivation Counseling	Behavioral Activation (BA) Counseling
1	Mini-Lozenge	BR	5Rs	BA
2	Mini-Lozenge	BR	5Rs	No BA
3	Mini-Lozenge	BR	No 5Rs	BA
4	Mini-Lozenge	BR	No 5Rs	No BA
5	Mini-Lozenge	No BR	5Rs	BA
6	Mini-Lozenge	No BR	5Rs	No BA
7	Mini-Lozenge	No BR	No 5Rs	BA
8	Mini-Lozenge	No BR	No 5Rs	No BA
9	No Mini-Lozenge	BR	5Rs	BA
10	No Mini-Lozenge	BR	5Rs	No BA
11	No Mini-Lozenge	BR	No 5Rs	BA
12	No Mini-Lozenge	BR	No 5Rs	No BA
13	No Mini-Lozenge	No BR	5Rs	BA
14	No Mini-Lozenge	No BR	5Rs	No BA
15	No Mini-Lozenge	No BR	No 5Rs	BA
16	No Mini-Lozenge	No BR	No 5Rs	No BA

“Breaking Addiction to Tobacco for Health (BREATHE) Study”  
 PI: [name], MPH, MBA; UW-CTRI Center Grant: 1P01CA180945-01.

\*Note. In factorial designs each main effect is tested; within each column, the shaded vs. non-shaded rows are compared.

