**Table 3. Motivation Study Schedule of Study Contacts**

Week	0	1	2	3	4	5	6	9	12	15	18	22	26	30	34	38	39	43	47	52
Visit	X																			
Assessment Call				X*		X*			X				X				X			X
IVR Calls			X		X		X	X		X	X	X		X	X			X	X	
BR counseling	X	X		X		X		X		X		X		X		X			X	
BA Counseling	X	X		X		X		X		X		X		X		X			X	
5Rs Counseling	X									X				X					X	
Mini-Lozenge	X								X				X			X				

\*Medication use and AE Assessments only

**Cessation Phase.** Participants who decide to quit during the first 9 months of the Motivation Phase treatment period will receive a cessation treatment. The cessation treatment includes in-person counseling sessions at Days -7, 7 and 14, and a counseling phone call on the target quit day (TQD). Participants will receive 8 weeks of medication at Day -7 (see Table 4). Two follow up assessments will occur at 28 and 56 days post TQD to assess for medication use and symptoms for the full duration of the medication schedule. *Participants who chose to receive the cessation treatment will still receive all Motivation Phase phone and IVR assessments to permit standardized assessments for all Motivation Phase participants.*

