### **The Intervention Components**

All 3 studies will use as their primary interventions nicotine replacement therapy for treating smokers and one or more specific types of counseling. They will also employ the same research staff (referred to as health counselors) with each health counselor trained to provide all types of counseling. The research will use specific quality/fidelity assurance strategies that include: intensive case manager training in counseling and ethical conduct, mock sessions, review of audiotapes, and meetings to discuss safety, confidentiality, and treatment fidelity. Health counselors will meet every other week for clinical supervision with a clinical psychologist investigator to review the study protocol and address treatment issues. A common database provides guidance on the counseling content, medication and assessments to be provided at each contact. Such procedures have produced excellent treatment delivery fidelity in our recent work. The distinct intervention components are detailed below.

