### ***Motivation Study***

Participants in the Motivation Study may receive treatment during 2 phases: Motivation and Cessation. While all participants will receive Motivation treatment, participation in the Cessation phase of the research depends on whether participants decide they would like to quit smoking during the Motivation phase.

***Motivation Phase.*** All participants will start the study in the Motivation Phase.

**Nicotine Replacement Therapy (NRT).** Participants randomly assigned to the Mini-Lozenge condition will use either the 2- or 4-mg doses (smoke within 30 min of waking = 4mg; smoke more than 30 min after waking = 2mg—as per package insert). Starting Spring 2018 we started to screen individuals who would be prescribed mini-lozenges for soy allergens prior to

“Breaking Addiction to Tobacco for Health (BREATHE) Study”

PI: [name], MPH, MBA; UW-CTRI Center Grant: 1P01CA180945-01.

dissemination to prevent allergic reaction AEs - per the ML new package insert. Participants will be instructed to use the product for 12 months and to use it in a scheduled manner consistent with the 2008 PHS Guideline; they will be instructed to use one Mini-Lozenge every 1-2 hours and up to 12 daily, with a goal of using at least 5 daily. Participants will receive 12-weeks of medication at Visit 1 and will be sent additional medication after the assessment calls at Weeks 12, 26, and 39. The case manager will provide use instructions, teach participants to detect symptoms of nicotine toxicity, and encourage them to reduce smoking and/or NRT use to avoid these symptoms. All participants will be given an information sheet that conveys all medication instructions as well as a phone number to call if they have concerning side effects or other questions about their medication. All participants will be told to promptly report any difficulty, side effects or allergic reactions, and we will consult with participants as per good clinical practice to address any problems they have with NRT use. In some cases we may counsel participants to stop using NRT if they develop significant side effects (e.g., vomiting). The case manager will refer the patient to their primary care physician should the patient require medical consultation.

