## PROTOCOL

### “Breaking Addiction to Tobacco for Health (BREATHE) Study”

PI: [name], MPH, MBA; UW-CTRI Center Grant: 1P01CA180945-01.

a Decisional Balance Questionnaire about smoking, assessments about whether they have been encouraged to quit, and assessments of recent quit attempts and plans for future quitting. Participants will complete 4 assessment calls at Weeks 12, 26, 39 and 52 (see Table 11). Only selected items from the above scales will be used for the subsequent assessment calls. Medication usage and side effects will be assessed at every study contact for participants using Nicotine Mini-Lozenge. NRT use and smoking will be assessed at each contact using the timeline follow back procedures.

**Intensive Longitudinal Data (ILD).** Participants will receive 11 brief, automated assessment calls over 52 weeks after Visit 1 (see Table 3 for schedule). The assessment schedule will continue even if a participant receives the cessation treatment to permit standardized assessments for all participants. The 3-4 min calls will occur shortly before bedtime, based on participants’ self-reported sleep times. This has resulted in acceptable call times in our previous research. The calls will assess: withdrawal symptoms (selected items from the Wisconsin Smoking Withdrawal Scale, including craving); positive and negative affect assessed via items from the PANAS; time to first cigarette in the morning; any smoking and use during the day of the call and during the preceding 7 day period; alcohol use, quit attempts and plans for quitting; pleasure from events; medication use; intrinsic motivation to quit or reduce smoking; and self-efficacy. Missed or deferred calls will be reinitiated in 15-minute intervals. Eligible participants must have access to a phone (either cell or land line). This assessment burden is much less than has been used successfully in many other studies, and research has shown that ILD/ecological momentary assessment produces modest assessment reactivity. Our prior experience shows that IVR systems yield high quality information with response rates exceeding 80%, even among primary care patients.

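### The Motivation Study rule for delivering the Week 3 and 5 medication and adverse-event checks gives no route to participants assigned 5Rs counseling without BR or BA

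*Combined protocol and SAP*

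**What the plan says.** Under Study Procedures, the Motivation Phase text states that medication-use and AE assessments take place "either during the Week 3 and 5 counseling calls, or alone if the participant is not randomized to receive any counseling". There are two routes: inside a counseling call at those weeks, or as a call of their own for participants with no counseling assigned.

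The same section sets the counseling load. BR and BA each have a Week 0 session and nine phone sessions. For 5Rs: "Participants receiving 5Rs Motivation Counseling will receive 1 in-person session at Week 0 followed by 3 phone sessions". It lists the assessment calls that all participants receive at Weeks 12, 26, 39 and 52, and does not include Weeks 3 and 5.

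Table 3 marks assessment calls at Weeks 3 and 5, footnoted "Medication use and AE Assessments only", without naming any condition as excluded.

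Table 1 crosses all four factors. Condition 6 is Mini-Lozenge, No BR, 5Rs, No BA. Condition 14 is the same without the lozenge.

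The Data Collection section for this study adds: "Medication usage and side effects will be assessed at every study contact for participants using Nicotine Mini-Lozenge".

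**The concern.** The delivery rule treats having any counseling as equivalent to having counseling calls at Weeks 3 and 5. For 5Rs this is false. A participant with 5Rs alone has counseling, so the stand-alone route is closed, and has no counseling call at those weeks, so the in-call route is closed too.

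What is at stake is the early staff safety check for lozenge users in that position. They enter the study with no plan to quit in the next month, so they may still be smoking, and they are told they may use up to 12 lozenges a day. The protocol acknowledges that acute nicotine toxicity is possible. A scheduler or database that takes the sentence at its word would leave out the Week 3 and 5 calls for the whole cell, not just for occasional individuals.

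**Working it through.** **Inputs.** Contact weeks from Table 3; the 16 conditions from Table 1; N = 512 and 256 per factor level from the Motivation Study power section. Equal allocation to the 16 cells is assumed; this agrees with 256 per level.

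**Step 1: contact weeks, read by column from Table 3, checked against the counts in the text.**

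| Row | Weeks | Contacts | Text |
|---|---|---|---|
| BR | 0, 1, 3, 5, 9, 15, 22, 30, 38, 47 | 10 | 1 + 9 |
| BA | 0, 1, 3, 5, 9, 15, 22, 30, 38, 47 | 10 | 1 + 9 |
| 5Rs | 0, 15, 30, 47 | 4 | 1 + 3 |

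The counts agree, so the columns have been read correctly. Only BR and BA have calls at Weeks 3 and 5.

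**Step 2: apply the two routes to every condition.** Cell size = 512 / 16 = 32.

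| Route under the current sentence | Conditions | Participants |
|---|---|---|
| Inside a Week 3/5 counseling call (any BR or BA) | 1, 2, 3, 4, 5, 7, 9, 10, 11, 12, 13, 15 | 12 × 32 = 384 |
| Alone (no counseling) | 8, 16 | 2 × 32 = 64 |
| Neither | 6, 14 | 2 × 32 = 64 |
| Total | 16 | 512 |

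Among the eight lozenge cells, six (192) are covered in-call, one (32, Condition 8) alone, and one (32, Condition 6) by neither. Condition 6 is 32 / 256 = 12.5% of those assigned lozenges.

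**Step 3: what contacts Condition 6 has before Week 12 under the literal sentence.** After Week 0 its next 5Rs session is Week 15. The safety row of Table 11 has entries only at Weeks 12, 26, 39 and 52. IVR calls fall at Weeks 2, 4, 6 and 9. Their item list includes "alcohol use, quit attempts and plans for quitting; pleasure from events; medication use; intrinsic motivation to quit or reduce smoking; and self-efficacy", along with withdrawal, affect and smoking items; it covers medication use but has no AE item. The first scheduled staff AE check is therefore Week 12, against Week 3 under Table 3. A participant who enters the Cessation Phase earlier has staff contacts sooner.

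**Step 4: do other sections supply the missing contact?** Data Collection, Protection Against Risk and the Data and Safety Monitoring Plan all require side-effect assessment at contacts that occur. None of them creates a contact at Week 3 or 5.

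**Step 5: test the replacement trigger.** If the stand-alone route applies to anyone assigned neither BR nor BA, it covers Conditions 6, 8, 14 and 16 (4 × 32 = 128), and the in-call route covers the other 12 (384). The total is 512, with exactly one route per condition.

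**The case against.** The strongest reply is that the contact schedule already answers the question. Table 3 has an assessment-call row separate from the counseling rows, it marks Weeks 3 and 5 for no particular condition, and a footnote limiting the content to medication use and AEs describes a call that can stand alone. The Data Collection rule then supplies the content of that contact. On this view the words about counseling simply mean counseling at those calls. There are also other safeguards: "All participants will be told to promptly report any difficulty, side effects or allergic reactions", participants get an information sheet and a phone number, counselors teach them to recognize nicotine toxicity, and the IVR calls ask about medication use.

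Much of this stands. Table 3 probably shows the intent, and the safeguards keep the severity low. It does not settle the matter. The marks in Table 3 generally do not carry the condition limits that apply to them, so an unrestricted mark does not prove that every cell gets the call. The Motivation Phase text leaves Weeks 3 and 5 out of its list of calls for all participants. The sentence that says how these checks are delivered still provides no route for 5Rs alone.

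A reader might also infer that the stand-alone route is too wide, because it sends medication and AE calls to Condition 16, which has no study lozenge in this phase, and that the route should be limited to lozenge users. The documents do not support that. The Data Collection section assesses NRT use at each contact in a sentence not confined to the lozenge arm, and Table 3 excludes no cell. Limiting the route to lozenge users would leave Conditions 14 and 16 without one.

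**Conclusion.** The delivery rule is wrong as written. It gives no route to two of the 16 conditions, about 64 participants, of whom about 32 (Condition 6) have study medication. Followed literally, it moves Condition 6's first scheduled staff AE check after Week 0 from Week 3 to Week 12, unless the participant enters the Cessation Phase first. The participant counts assume equal allocation; the finding that Conditions 6 and 14 fit neither route depends only on Tables 1 and 3 and the sentence itself.

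A reader might go further and conclude that these participants were meant to go unchecked, or that checks were in fact missed. Neither is shown. Table 3 points the other way on intent, and nothing in the documents says how the scheduling was coded.

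Severity is low. No outcome, power figure or planned comparison changes.

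**What to change.** Change the condition on the second route so that the check is delivered alone to every participant assigned neither BR nor BA counseling, instead of only to those with no counseling at all. No restriction to lozenge users is needed.

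Then confirm that the scheduling system uses the same trigger. The Intervention Components section says "A common database provides guidance on the counseling content, medication and assessments to be provided at each contact", so this is the place where a literal coding of the present sentence would take effect.

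The cost is one clause, one check of the scheduling rule, and at most two short calls per participant in Conditions 6 and 14: 64 × 2 = 128 calls, of which 32 × 2 = 64 go to lozenge users. Table 3 already shows these calls.

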**Table 3. Motivation Study Schedule of Study Contacts**

Week	0	1	2	3	4	5	6	9	12	15	18	22	26	30	34	38	39	43	47	52
Visit	X																			
Assessment Call				X*		X*			X				X				X			X
IVR Calls			X		X		X	X		X	X	X		X	X			X	X	
BR counseling	X	X		X		X		X		X		X		X		X			X	
BA Counseling	X	X		X		X		X		X		X		X		X			X	
5Rs Counseling	X									X				X					X	
Mini-Lozenge	X								X				X			X				

\*Medication use and AE Assessments only

**Cessation Phase.** Participants who decide to quit during the first 9 months of the Motivation Phase treatment period will receive a cessation treatment. The cessation treatment includes in-person counseling sessions at Days -7, 7 and 14, and a counseling phone call on the target quit day (TQD). Participants will receive 8 weeks of medication at Day -7 (see Table 4). Two follow up assessments will occur at 28 and 56 days post TQD to assess for medication use and symptoms for the full duration of the medication schedule. *Participants who chose to receive the cessation treatment will still receive all Motivation Phase phone and IVR assessments to permit standardized assessments for all Motivation Phase participants.*

**Table 4. Motivation Study Schedule of Treatment Contacts for Participants who Choose to Quit Smoking**

Day	-7	TQD	7	14	28	56
In-Person Counseling	X		X	X		
Phone Counseling		X				
Medication	X					
Assessment					X	X

### **Cessation Study**

After the in-person baseline session, participants assigned to the Modern Usual Care (M-UC) will have no other treatment visits or calls, other than the single call from the Wisconsin Tobacco Quit Line. However, participants in this condition will receive the 6 assessment calls at Weeks 4, 8, 16, 26, 39 and 52.

Participants in the Abstinence-Optimized Cessation Treatment (AOCT) will attend three additional visits at 1 week pre-quit, on the Target Quit day (TQD), and 1 week post-quit, during which they will receive the in-person counseling (see Table 5). In addition, AOCT participants will receive 8 counseling calls at Weeks 3, 4, 6, 8, 10, 14, 18, and 22 as well as 7 or 11 automated calls that encourage medication adherence at Days 1, 3, 10, 17, 24, 31 and 45 (those who are still smoking at Week 8 will receive 4 additional automated adherence calls to encourage medication use at Days 73, 101, 126 and 154). Participants in AOCT will receive 3 weeks of pre-quit nicotine mini-lozenges at Visit 1 and will receive nicotine mini-lozenges and

## PROTOCOL

### “Breaking Addiction to Tobacco for Health (BREATHE) Study”

PI: [name], MPH, MBA; UW-CTRI Center Grant: 1P01CA180945-01.

nicotine patches 1 week before their quit day. Participants who are still using the medication will receive more medication following the 8-week and 16-week assessment calls.

**Table 5. Cessation Study Schedule of Treatment Contacts for AOCT Participants.**

Day	-21	-7	TQD	1	3	7	10	17	24	28	31	45	56	73	101	112	126	154
Week	-3	-1	0	1	1	1	2	3	4	4	5	6	8	10	14	16	18	22
Visit	1	2	3			4												
Medication	X	X				X							X			X		
In-Person Counseling		X	X			X												
Maintenance Calls								X		X		X	X	X	X		X	X
Automated Calls*				X	X		X	X	X		X	X		x	x		x	x
IVR Calls**		X	X	X	X	X	X											
Assessment Calls†										X			X			X		

\*Automated calls will be discontinued after Week 6 for those who report abstinence at their Week 8 assessment call

\*\*IVR calls will be daily from 1 week pre-quit through 2 weeks post-quit.

†Additional assessment calls will occur at Weeks 26, 39 and 52. Further, participants reporting abstinence at 26 weeks will be invited to come to the clinic to provide a breath sample for biochemical confirmation of abstinence.

### **Long-term Quitting Study**

This study has three potential phases: Initial Cessation (also called the “Quit Phase”), Relapse Recovery (RR) Preparation (also called the “Preparation Phase”), and RR Cessation (also called the “New Quit Phase”). While all participants will receive the same Initial Cessation Treatment, participation in the subsequent phases of the research depends on participant response to the prior phase and on what RR Preparation condition they are randomized to.

**Initial Cessation Phase.** All participants will receive the same Initial Cessation Treatment, and includes an in-person counseling session at Day -7 and counseling phone calls on Day 7, and Day 14 (see Table 6). There will also be assessment calls from research staff (see Table 6). *Initial Cessation Assessments will stop once a participant is randomized to the RR Preparation treatment or Control conditions.*

**Table 6. Long-Term Quitting Study Initial Cessation Phase Schedule of Treatment Contacts\***

Day	-7	-1	1	3	7	14	28	56	84	112	140	168
Week	-1				1	2	4	8	12	16	20	26
Visit	X											
Medication	X											
In-Person Counseling	X											
Phone Counseling					X	X						
IVR Calls		X	X	X								
Assessment Calls					X†	X†	X	X	X	X	X	X

\*All treatment and assessments will be discontinued for those who relapse between the quit date and 6 months postquit. (Relapse criteria can first be met at 6 days after the target quit day.) †These assessment calls will be combined with the counseling calls.

## PROTOCOL

### “Breaking Addiction to Tobacco for Health (BREATHE) Study”

PI: [name], MPH, MBA; UW-CTRI Center Grant: 1P01CA180945-01.

**RR Preparation Phase.** Participants may enter the Relapse Recovery (RR) Preparation phase if relapse is detected during the initial cessation treatment for up to 6 months after the quit day via either counseling calls or assessment calls. If relapse is detected, the health counselor or student assessor will randomize the participant to one of the 3 RR Preparation intervention conditions via a dynamic real-time database. If the participant does not relapse or chooses not to enter the preparation phase during this 6 month period, they will not be eligible for the RR preparation phase.

If participants are assigned to the Preparation Control condition, they will be encouraged to continue the Initial Cessation treatment (if counseling sessions and/or medication remain) and to continue taking the study medication, but to contact the WTQL or talk to their referring clinician for additional treatment. Participants in the Preparation Control condition will be given WTQL contact information only the first time they report relapse. The RR Preparation Control participants will complete their RR Preparation baseline assessments at their first Standard Assessment Staff call at Week 1. They will also be asked to attend a visit at the 14 month mark to provide a CO sample if they claim abstinence at that time (abstinence demonstrated by a CO  $\leq$  5 ppm).

Participants assigned to an “active” RR Preparation condition (either Reduction or Recycling) will schedule a visit. At the visit, participants will complete RR baseline assessments, the nature of that treatment will be explained, future contacts will be described and scheduled, and treatment will be provided (Behavioral Reduction Counseling + nicotine mini-lozenges or Recycling Counseling); see Table 7. This first contact, where RR Preparation treatment begins for those in non-control conditions, is designated Preparation Day 0. Subsequent treatment contacts will be scheduled for such participants for Week 2 and Months 1, 3, 6, 9, & 11 post-Preparation Day 0. The contacts at Week 0 and Months 1 & 6 will be in-person visits; all other RR Preparation contacts will be by phone. However, if a participant cannot attend an in-person visit, a phone visit will be conducted instead.

All participants assigned to the non-control (active) RR Preparation conditions will receive Standard Assessment Staff calls (at Week 1 and Months 2, 4, 7, & 10) in addition to assessments that occur at RR Preparation treatment contacts (at Day 0, Week 2, and Months 1, 3, 6, 9, & 11). The phone assessments occurring at RR Preparation treatment contacts other than the Day 0 and Week 2 contacts will be brief, collecting primarily data on smoking since the last treatment contact. Finally, all RR Preparation participants (including those in the control condition) will participate in follow-up calls at Month 14; at Month 14 they will be asked to make a visit to provide a CO sample should they claim abstinence (see Table 7).

Preparation Week	Preparation Day 0 (Day 0)	1	2	4	8	10	12	16	24	28	32	36	40	41	43	56
Month	0			1	2		3	4	6	7	8	9	10		11	14
Visit	X			X					X							X†
Reduction or Recycling Counseling	X		X	X			X		X			X			X	

